#### 4.0 STUDY POPULATION

Version 4.0 Date: 08/21/2020

NCT02463799

The values for radium-223 in this protocol has been revised as per the US NIST standardization update (agreed on 17 Mar 2015)

To participate in this study, subjects must meet all inclusion criteria and none of the exclusion criteria.

#### **4.1 Inclusion Criteria**

**4.1.1** Written informed consent provided prior to the initiation of study procedures.

**4.1.2** Age  $\geq$  18 years.

**4.1.3** Histologically documented adenocarcinoma prostate cancer confirmed by a pathology report from prostate biopsy or a radical prostatectomy specimen. If prostatic tumor is of mixed histology,  $>$  50% of the tumor must be adenocarcinoma.

**4.1.4** Bone metastases as manifested by one or more lesions on a bone scan performed within 2 months of screening

**4.1.5** Castrate-resistant prostate cancer, in the setting of castrate levels of testosterone ( $\leq$  50 ng/dL), defined as current or historical evidence of disease progression concomitant with surgical castration or ADT, as demonstrated by two consecutive rises in PSA OR new lesions on bone scan:

PSA progression will be defined as 2 rising PSA values compared to a reference value, measured at least 7 days apart and the second value is  $\geq$  2 ng/mL [1]. It must be documented within 2 months of screening.

Appearance of one or more new areas of abnormal uptake on bone scan when compared to imaging studies acquired during castration therapy or against the precastration studies if there was no response. Increased uptake of pre-existing lesions on bone scan does not constitute progression. It must be documented within 4 months of screening.

**4.1.6** Serum PSA  $\geq$  2.0 ng/mL.

**4.1.7** Screening ECOG performance status  $\leq$  1.

**4.1.8** Asymptomatic or minimally symptomatic disease (no narcotic analgesic; other analgesics use is allowed)

**4.1.9** Prior abiraterone and enzalutamide are permitted, but not required.

**4.1.10** Concurrent osteoclast-inhibitory therapies (zoledronic acid, denosumab) are permitted if patients have been on a stable dose for at least 1 month

Version 4.0 Date: 08/21/2020

NCT02463799

The values for radium-223 in this protocol has been revised as per the US NIST standardization update (agreed on 17 Mar 2015)

**4.1.11** Adequate screening hematologic, renal, and liver function as evidenced by laboratory test results within the following ranges  $\leq 28$  days prior to registration:

- Absolute neutrophil count (ANC)  $\geq 1.5 \times 10^9/L$
- Platelet count  $\geq 100 \times 10^9/L$
- Hemoglobin  $\geq 10.0$  g/dL
- Total bilirubin level  $\leq 1.5$  x institutional upper limit of normal (ULN)
- Aspartate aminotransferase (AST) and alanine aminotransferase (ALT)  $\leq 2.5$  x ULN
- Creatinine  $\leq 1.5$  x ULN
- Albumin  $> 25$  g/L

## **4.2 Exclusion Criteria**

**4.2.1** The presence of known lung or liver metastases greater than 1.0 cm in long-axis diameter.

**4.2.2** The presence of lymphadenopathy greater than 3 cm in the short-axis diameter

**4.2.3** The presence of known brain metastases.

**4.2.4** Spinal cord compression, imminent long bone fracture, or any other condition that, in the opinion of the investigator, is likely to require radiation therapy and/or steroids for pain control during the active phase.

**4.2.5** Previous treatment with chemotherapy for mCRPC or chemotherapy for any reason within 6 months prior to registration. (Chemotherapy in the adjuvant setting or for hormone-sensitive prostate cancer is permitted, as long as it was completed more than 6 months before registration).

**4.2.6** Intention to receive chemotherapy within 6 months after enrollment in protocol therapy.

**4.2.7** History of radiation therapy, either via external beam or brachytherapy within 28 days prior to registration.

**4.2.8** Systemic radiotherapy with strontium-89, samarium-153, rhenium-186 or rhenium-188 for the treatment of bony metastases within previous 24 weeks

**4.2.9** Prior history of other cancers (except non-melanoma skin cancers or low-grade low-stage urothelial cancers), or other localized cancers without evidence of recurrence for at least 3 years.

**4.2.10** Use of prednisone or equivalent systemic corticosteroid within 2 weeks of sipuleucel-T. Use of inhaled, intranasal, intra-articular, and topical steroids is allowed. Oral or IV steroids to prevent or treat IV contrast reactions are allowed.

**4.2.11** Use of opioid analgesics for cancer-related pain

**4.2.12** Use of experimental drug within 4 weeks of treatment.

**4.2.13** Uncontrolled medical conditions including diabetes, heart failure, COPD, ulcerative colitis, or Crohn's disease.

**4.2.14** Uncontrolled fecal incontinence.

**4.2.15** Any medical intervention, any other condition, or any other circumstance which, in the opinion of the investigator, could compromise adherence with study requirements or otherwise compromise the study's objectives.

## **5.0 STUDY TREATMENTS**

### **5.1 Radium-223**

#### **5.1.1 Dosage Forms and Strength**

Radium-223 is available in single-use vials containing 6 mL of solution at a concentration of 1,000 kBq/mL (27 microcurie/mL) (1,100 kBq/mL (29.7 microcurie/mL) after implementation of the NIST update) at the reference date with a total radioactivity of 6,000kBq/vial (162 microcurie/vial) (6,600 kBq/vial (178 microcurie/vial) after implementation of the NIST update) at the reference date.

#### **5.1.2 Preparation**

Radium-223 is a ready-to-use solution and should not be diluted or mixed with any solutions. Each vial is for single use only. Parenteral drug products should be inspected visually for particulate matter and discoloration prior to administration, whenever solution and container permit.

#### **5.1.3 Dosage**

The dose regimen of radium-223 is 50 kBq (1.35 microcurie) (55 kBq/kg (1.49 microcurie/kg) after implementation of the NIST update) per kg body weight, given at 4 week intervals for 6 injections.

Version 4.0 Date: 08/21/2020

NCT02463799

The values for radium-223 in this protocol has been revised as per the US NIST standardization update (agreed on 17 Mar 2015)

The volume to be administered to a given patient should be calculated using the:

- Patient’s body weight (kg)
- Dosage level 50 kBq/kg body weight (55 kBq/kg after implementation of the NIST update) or 1.35 microcurie/kg body weight (1.49 microcurie after implementation of the NIST update)
- Radioactivity concentration of the product (1,000 kBq/mL; 27 microcurie/mL (1,100 kBq/mL after implementation of the NIST update; 29.7 microcurie/mL) at the reference date
- Decay correction factor to correct for physical decay of radium-223.

The total amount (volume to be drawn into the syringe) to be administered to a patient should be calculated as follows:

$$\text{Volume to be administered (mL)} = \frac{\text{Body weight (kg)} \times \text{dose (50 kBq/kg b.w)}^a}{\text{DK factor} \times 1,000 \text{ kBq (0.027 mCi)/mL}}^b$$

a 55 kBq/kg after implantation of the NIST update

b 1,100 kBq (29.7 microcurie)/mL after implantation of the NIST update

Decay Correction Factor Table

Days from Reference Date	Decay Factor	Days from Reference Date	Decay Factor
-14	2.296	0	0.982
-13	2.161	1	0.925
-12	2.034	2	0.870
-11	1.914	3	0.819
-10	1.802	4	0.771
-9	1.696	5	0.725
-8	1.596	6	0.683
-7	1.502	7	0.643
-6	1.414	8	0.605
-5	1.330	9	0.569
-4	1.252	10	0.536
-3	1.178	11	0.504
-2	1.109	12	0.475
-1	1.044	13	0.447
		14	0.420

The Decay Correction Factor Table is corrected to 12 noon Central Standard Time (CST). To determine the decay correction factor, count the number of days before or after the reference date. The Decay Correction Factor Table includes a correction to account for the 7 hour time

Version 4.0 Date: 08/21/2020

NCT02463799

The values for radium-223 in this protocol has been revised as per the US NIST standardization update (agreed on 17 Mar 2015)

difference between 12 noon Central European Time (CET) at the site of manufacture and 12 noon US CST, which is 7 hours earlier than CET.

Immediately before and after administration, the net patient dose of administered radium-223 should be determined by measurement in an appropriate radioisotope dose calibrator that has been calibrated with a National Institute of Standards and Technology (NIST) traceable radium-223 standard (a new reference vial will be sent to each center corresponding to the updated NIST reference material) and corrected for decay using the date and time of calibration. The dose calibrator must be calibrated with nationally recognized standards, carried out at the time of commissioning, after any maintenance procedure that could affect the dosimetry and at intervals not to exceed one year.

Each center must perform the Radium Ra 223 dichloride dial setting on their relevant dose calibrator(s) (upon notification by Bayer each center is required to update the dial setting to correspond to the new NIST standard). The current dial settings are to remain in effect until Bayer obtains FULL approval from the FDA for implementation. In preparation for implementation of the NEW dial setting, the clinical study center will receive a sealed vial labeled NIST standard containing a Radium Ra 223 dichloride solution for calibration only. The vial is identical to the vials used for study treatment. The amount of Radium Ra 223 dichloride in the vial will be stated on the label. Instructions for the dial setting, including the calibration log form, will be enclosed with the dispatch of the calibration sample.

All sites will be notified by Bayer when FINAL regulatory approval from the FDA is in place and the updated NIST standardization is to be implemented.

#### **5.1.4 NIST Standardization Update**

The qualification of radium-223 radioactive in Xofigo (radium-223 dichloride; BAY 88-8223) is based on the primary standardization performed by the US NIST. National Institute of Standards and Technology prepares the standard reference material (SRM) using an official dial setting (primary standardization) as published [20]. The NIST SRM is used to calibrate the instruments in production and quality control for both the drug substance and drug product. Additionally, the NIST SRM is used to prepare the NIST traceable Ra-223 reference materials which are then sent to the end-users (e.g., nuclear medicine laboratory physicians or technicians) for dial-setting of their dose calibrators, to allow verification of the patient dose.

In 2014, NIST performed a re-assessment of the primary standardization based on preliminary information suggesting a potential discrepancy of approximately 8-10% between the published NIST primary standardization [20] and results obtained by other national metrology institutes (United Kingdom, Germany, Japan). After completion of the re-assessment, NIST reported their findings [21] and had issued a revised NIST SRM in 2015. The discrepancy in the NIST

Version 4.0 Date: 08/21/2020

NCT02463799

The values for radium-223 in this protocol has been revised as per the US NIST standardization update (agreed on 17 Mar 2015)

standardization was determined to be -9.5% between activity values obtained using the old reference standard relative to the new primary standardization. Consequently, the current numerical values need to be corrected by approximately +10.5%

The current NIST standard for radium-223 dichloride will remain in effect until the FDA has fully approved the regulatory variation submitted for Xofigo and is anticipated in the 2nd quarter of 2016. All sites are expected to begin preparation for the updated NIST standardization and obtain all necessary IRB approvals. Bayer will continue to notify sites about the status of the regulatory approval and the date that the updated NIST standardization is to be implemented. Upon notification, and prior to the implementation, all sites are expected to add a new dial setting to their dose calibrators for the new NIST standardization for radium-223 dichloride, which should be documented on the appropriate study forms.

The change in the numerical description of the patient's dose, product strength and labeled vial activity does not impact the safety or efficacy of Xofigo. The change in the NIST radium-223 standard has no impact on subjects; dose subjects are receiving, and will continue to receive. Subjects will receive the same actual dose and volume that was studied in Study 15245 (BCI-06 dosimetry study) and is associated with the proven safety and efficacy of radium-223 dichloride, though the stated nominal radiation dose received is being updated to reflect the new standard. The formula for the calculation of the volume to be administered has to be changed respectively. (see dose section) Subjects who are on-treatment at the time the new NIST reference standard goes into effect should be notified of this change and should be required to sign a Patient Information Sheet to acknowledge that they have received information on the updated NIST standard calibration. All patients randomized after the new reference standard is in effect should sign a revised Informed Consent Form that contains the updated NIST standardization.

### **5.1.5 Administration**

Radium-223 should be administered by slow IV injection over 1 minute. The IV access line or cannula should be flushed with isotonic saline before and after injection of radium-223.

### **5.1.6 Handling and Patient Protection**

Radium-223 is primarily an alpha emitter, with a 95.3% fraction of energy emitted as alpha-particles. The fraction emitted as beta-particles is 3.6%, and the fraction emitted as gamma-radiation is 1.1%. The external radiation exposure associated with handling of patient doses is expected to be low, because the typical treatment activity will be below 8,000 kBq (216 microcurie). (8,800 kBq (238 microcurie) after implementation of the NIST update) In keeping with the **As Low As Reasonably Achievable (ALARA)** principle for minimization of radiation exposure, it is recommended to minimize the time spent in radiation areas, to maximize the distance to radiation sources, and to use adequate shielding. Any unused product or materials

Version 4.0 Date: 08/21/2020

NCT02463799

The values for radium-223 in this protocol has been revised as per the US NIST standardization update (agreed on 17 Mar 2015)

used in connection with the preparation or administration are to be treated as radioactive waste and should be disposed of in accordance with local regulations. The gamma radiation associated with the decay of radium-223 and its daughters allows for the radioactivity measurement of radium-223 and the detection of contamination with standard instruments.

#### General warning

Radium-223 should be received, used and administered only by authorized persons in designated clinical settings. The receipt, storage, use, transfer and disposal of radium-223 are subject to the regulations and/or appropriate licenses of the competent official organization.

Radium-223 should be handled by the user in a manner which satisfies both radiation safety and pharmaceutical quality requirements. Appropriate aseptic precautions should be taken.

#### Radiation protection

The administration of radium-223 is associated with potential risks to other persons (e.g., medical staff, caregivers and patient's household members) from radiation or contamination from spills of bodily fluids such as urine, feces, or vomit. Therefore, radiation protection precautions must be taken in accordance with national and local regulations.

#### For drug handling

Follow the normal working procedures for the handling of radiopharmaceuticals and use universal precautions for handling and administration such as gloves and barrier gowns when handling blood and bodily fluids to avoid contamination. In case of contact with skin or eyes, the affected area should be flushed immediately with water. In the event of spillage of radium-223, the local radiation safety officer should be contacted immediately to initiate the necessary measurements and required procedures to decontaminate the area. A complexing agent such as 0.01 M ethylene-diaminetetraacetic acid (EDTA) solution is recommended to remove contamination.

#### For patient care

Whenever possible, patients should use a toilet and the toilet should be flushed several times after each use. When handling bodily fluids, simply wearing gloves and hand washing will protect caregivers. Clothing soiled with radium-223 or patient fecal matter or urine should be washed promptly and separately from other clothing.

## **5.2 Sipuleucel-T**

Version 4.0 Date: 08/21/2020

NCT02463799

The values for radium-223 in this protocol has been revised as per the US NIST standardization update (agreed on 17 Mar 2015)

The patients included in the study are scheduled for standard treatment with commercially available sipuleucel-T according to institutional practice and the approved product information (available at; <http://www.dendreon.com/prescribing-information.pdf>).

### **5.2.1 Leukapheresis and Infusion Scheduling**

Leukapheresis appointments will be scheduled at approximately 2-week intervals. The clinical trial site will schedule the subject's infusion appointments based on this schedule. If the subject is subsequently deemed ineligible, the clinical trial site will be informed and the leukapheresis and infusion appointments will be canceled.

### **5.2.2 Leukapheresis**

The collection of blood cells to manufacture sipuleucel-T is analogous to that for autologous blood transfusions. Subjects undergo a standard 1.5 to 2.0 blood volume leukapheresis to harvest PBMCs (primarily lymphocytes and monocytes).

### **5.2.3 Product Quality assessment**

Prior to infusion, small samples (3% to 4%) of cellular components from pre and post-culture (PA2024) cells will be used to assess product potency as part of the normal sipuleucel-T manufacturing process. Sipuleucel-T quality assessments include total TNC count, CD54+ cell count and CD54 upregulation.

### **5.2.4 Sipuleucel-T Infusion**

Each sipuleucel-T dose is released for infusion approximately 3 days following the leukapheresis procedure. Subjects will be infused according to the infusion guidelines (available at; <http://www.dendreon.com/prescribing-information.pdf>).

### **5.2.5 Sipuleucel-T Product Failures and Leukapheresis Rescheduling**

In the event that a subject's leukapheresis procedure fails, sipuleucel-T does not meet quality release specifications, or infusion is not possible for any other reason, the subject may be scheduled to undergo a repeat leukapheresis procedure. A minimum of 2 days must have elapsed since the last leukapheresis procedure. Scheduling will depend upon capacity of the leukapheresis and Dendreon manufacturing facilities. If the second or third leukapheresis appointment is delayed or rescheduled for any reason, a physical examination and all other pre-leukapheresis procedures must be repeated within the 5 days prior to the next leukapheresis procedure.

### **5.3 Treatment Compliance**

Study drugs will be administered or dispensed only to eligible patients under the supervision of the investigator or identified sub-investigator(s). The appropriate study personnel will maintain records of study drug receipt and dispensing.

### **5.4 Drug Accountability**

Study drugs should be kept in a secure place and must be administered only to patients in the trial. A log of study drug (received, administered to patients and destroyed) must be maintained and signed by the person responsible for drug handling at each center. Study site/institution personnel will record all study drug administered during this trial on the drug-dispensing log. Description of monitoring of the overall drug accountability will be detailed in study and site specific procedures.

The nuclear medicine specialist or radiation oncologist at the center is responsible for drug accountability for radium-223. When the drug accountability has been monitored, the vials can be destroyed in accordance with hospital procedure for the handling of radioactive material, normally after storage for 4 months from date of receipt (>10 half-lives) before disposal; they may then be disposed as non-radioactive waste

### **5.5 Concomitant Medications**

Subjects should receive full supportive care, including transfusions of blood and blood products, antibiotics, antiemetics, or other therapies, in accordance with standard practice at the clinical trial site. Subjects receiving ADT, bisphosphonate therapy such as zoledronic acid (Zometa®), or denosumab (Xgeva®) at the time of registration should continue the therapy at a stable dose during radium-223 treatment.

All concomitant medications administered from screening through the last research visit at week 58, including indication, dose, route, frequency and treatment dates, will be recorded in the subject's medical record and on the CRF. After the last research visit at week 58, only anticancer therapies will be recorded. The first opioid taken for cancer-related pain will be recorded, regardless of when it is started.

### **5.6 Prohibited and/or Restricted Treatments**

Subjects on ADT must continue this therapy until the post-treatment visit or disease progression, whichever occurs first.

The following medications and interventions must not be initiated until the completion of radium-223 treatment or disease progression, whichever occurs first:

- Investigational vaccines or other investigational products.
- Ipilimumab or nivolumab.
- Hemibody radiation

Glucocorticoid-containing treatments should be minimized to the equivalent dose of prednisone 10mg daily or less if feasible for the 3 months following sipuleucel-T. Use of inhaled, intranasal, intra-articular, and topical steroids is acceptable, as well as a short course (i.e.,  $\leq 1$  day) of prophylactic steroid therapy prior to administration of IV contrast for CT imaging.

## **5.7 Discontinuation from Study Treatments or Assessments**

### **5.7.1 Patient withdrawal**

In accordance with the Declaration of Helsinki, patients have the right to withdraw from the study at any time for any reason, without prejudice to their medical care. The investigator also has the right to withdraw patients from the study for any of the following reasons:

- Consent withdrawal by the subject for any reason.
- Occurrence of AEs, if discontinuation of study medication is considered necessary by the Investigator and/or patient.
- The subject develops any condition requiring a prohibited treatment (Section 5.6).
- Lack of patient compliance
- Protocol violation.
- Study termination.
- The subject is lost to follow-up.
- Progressive disease (patients will only come off study after meeting PCWG2 and/or RECIST criteria for radiographic progression and not for PSA)

Subjects who withdraw consent, or lose the ability to freely provide consent, will be followed by the investigator for survival every 3 months using the Social Security Death Index (SSDI) and National Death Index (NDI). Date of death, where available, will be recorded in the subject's medical record and on the CRF.

Whenever possible, subjects discontinuing from the study will undergo a post-treatment visit. All AEs considered by the investigator to be related to study treatment(s) that are ongoing at the time of discontinuation will be followed by the investigator until resolution or until the subject returns to baseline. The investigator should make every reasonable attempt to ensure that the subject is

contacted (via telephone or during a post-treatment visit) to obtain the final status of any AEs and concomitant medications.

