## 5.9 Disease Progression

Disease progression is determined by the investigator per the definition below. The earliest date of disease progression will be recorded in the subject’s medical record and on the CRF. Following disease progression, all study treatments will cease, the subject will undergo a post-treatment visit and will be treated at the investigator’s discretion.

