### **6.7.1 Anticancer Therapies**

All anticancer therapies received prior to screening and through the end of the follow-up will be recorded in the subject's medical record and on the CRF. Anticancer therapies include, but are not limited to, radiation, chemotherapy, hormone therapy, investigational cancer therapies, all other systemic therapies, and surgery. The start/stop date and dose of anticancer therapies will be recorded.

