#### Exploratory Objectives:

- Median time to PSA progression based on Prostate Cancer Working Group 2 (PCWG2) criteria [1]:
  - in patients with no PSA decline from baseline as:  $\geq 25\%$  increase from the baseline value and an increase in absolute value of  $\geq 2$  ng/mL, at least 12 weeks from baseline
  - in patients with an initial PSA decline from baseline as:  $\geq 25\%$  increase and an absolute increase of  $\geq 2$  ng/mL above the nadir value, which is confirmed by a second value obtained three or more weeks later
- Median time to ALP progression.
  - in patients with no ALP decline from baseline as:  $\geq 25\%$  increase from the baseline value, at least 12 weeks from baseline
  - in patients with an initial ALP decline from baseline as:  $\geq 25\%$  increase above the nadir value, which is confirmed by a second value obtained three or more weeks later.
- Median time to pain progression defined as use of opioid analgesics for cancer-related pain.
- Median time to occurrence of first skeletal related event (SRE):
  - the use of external beam radiotherapy to relieve skeletal symptoms or the occurrence of new symptomatic pathological bone fractures (vertebral or non-vertebral) or the occurrence of spinal cord compression or a tumor related orthopedic surgical intervention.
- Median time to occurrence of first start of chemotherapy use.

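### Sections 5.7.1 and 5.9 do not say what is collected after radiographic progression, which leaves skeletal events and the later immune samples exposed

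*Combined protocol and SAP*

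**What the plan says.** **Leaving the study.** Section 5.7.1 introduces its list with "The investigator also has the right to withdraw patients from the study for any of the following reasons", and one entry is "Progressive disease (patients will only come off study after meeting PCWG2 and/or RECIST criteria for radiographic progression and not for PSA". Section 5.9 adds: "Following disease progression, all study treatments will cease, the subject will undergo a post-treatment visit". After that, management is left to the investigator and no further assessment is named.

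**Follow-up after leaving.** Section 5.7.1 states: "Subjects who withdraw consent, or lose the ability to freely provide consent, will be followed by the investigator for survival every 3 months". Section 5.8 says the same for men lost to follow-up. For any man who discontinues, 5.7.1 also asks that ongoing related adverse events be followed and that the final status of adverse events and medications be sought. No sentence covers chemotherapy, skeletal events or immune samples in a man who left for progression. By contrast, Section 5.7.2 expressly keeps men who stop only sipuleucel-T in the active-phase assessments.

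**Text pointing the other way.** Section 5.5: "The first opioid taken for cancer-related pain will be recorded, regardless of when it is started". Section 6.7.1: "All anticancer therapies received prior to screening and through the end of the follow-up will be recorded", where the definition includes radiation, chemotherapy and surgery. Section 3.0 schedules contacts every 3 months for a further year, but only after the week-58 visit. Their content is safety, related adverse events, survival, PSA, first opioid use and anticancer therapies.

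**Endpoints that depend on this.** The exploratory list in Section 8.5.2 includes "Median time to occurrence of first start of chemotherapy use", time to first skeletal related event (SRE) and time to opioid use. The secondary immune endpoints run to week 52. Section 8.6.3 gives no censoring rule for a man who comes off study.

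**The concern.** The plan uses one phrase, coming off study, where it may mean only stopping study treatment. Read literally, a man whose scan shows progression has one more visit and then leaves the data. Section 8.6.1 supports that reading: it describes premature discontinuation as refusing further assessments, with survival a possible exception.

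Two things are at stake.

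- **Time-to-event endpoints.** If men are censored when they progress, the censoring is related to prognosis. A Kaplan-Meier median for a later event such as first SRE would then tend to be too long.
- **Late immune results.** Samples after the detecting scan would come only from men without detected progression. Section 1.1 reports that immune response to sipuleucel-T correlates with survival, so this subset may well be selected on the quantity being measured.

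**Working it through.** **1. The plan's own figure.** The documents give no figure for this point. The only related one is the 80% power for week 6 in Section 8.2 (15 per arm, 3.6-fold ratio, log SD 1.4, one-sided 0.05). With ln 3.6 = 1.281 and SE = 1.4 × √(2/15) = 0.511, z = 1.281/0.511 − 1.645 = 0.86, which gives power of 80.5% (78.8% by the noncentral t). The figure reproduces.

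**2. Is the primary sample affected?** Section 6.1 places the first sipuleucel-T infusion at Arm 1 week 6 and allows it anywhere between the radium-223 infusions at weeks 4 and 8. The week-6 sample is therefore at study week 12 (range 10 to 14), before the Arm 1 scan at week 16. In Arm 2 it is at week 6, before the scan at week 10. On scheduled scans it is untouched.

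**3. What is captured after progression, item by item**

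| Item | Text that would capture it | Status for a man off study |
|---|---|---|
| First opioid | 5.5, at any time | Contradicts 5.7.1; not a proven loss |
| First chemotherapy | 6.7.1, to end of follow-up | Unsettled: follow-up is tied to week 58 |
| SRE: radiotherapy, surgery | 6.7.1, as anticancer therapy | Unsettled, and only part of the SRE definition |
| SRE: fracture, cord compression | 6.6.1 records only treatment-related events after week 20 | Not in the schedules or the follow-up list |
| Immune samples after the detecting scan | Schedule in 6.1 only | No statement that they continue |

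Two partial routes exist for fracture and cord compression. Section 5.9.2.1 counts them as clinical progression, but 5.9 records only the earliest progression date, so one that follows radiographic progression adds nothing. Section 7.3 asks more broadly than 6.6.1 for all adverse events on study, but ends 30 days after termination unless causality is suspected.

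**4. Size for the immune samples.** Assumptions, not from the documents: exponential radiographic progression with a median of 20 to 26 weeks, every progressor leaving at the scan that detects it, and no other losses. A sample is lost if progression was detected at a scan before it, so the share gone is 1 − 2^(−s/m), where s is the last earlier scan and m the median. Arm 2 scans per Section 3.0 are at weeks 10, 26, 39 and 52.

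| Sample week | s | Gone, m = 26 | Gone, m = 20 | Left of 15 |
|---|---|---|---|---|
| 14 and 26 | 10 | 23% | 29% | 10.6 to 11.5 |
| 39 | 26 | 50% | 59% | 6.1 to 7.5 |
| 52 | 39 | 65% | 74% | 3.9 to 5.3 |

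For Arm 1 the scan before the sample 26 weeks after first sipuleucel-T is at study week 16: 1 − 2^(−16/26) = 35% and 1 − 2^(−16/20) = 43%. With medians of 4 to 12 months, the Arm 2 numbers left of 15 are 10.1 to 13.1 (weeks 14 and 26), 5.3 to 10.6 (week 39) and 3.2 to 8.9 (week 52).

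The Arm 2 schedule table, as extracted, marks the first on-study imaging at week 14 instead of 10. The loss before week 26 would then be 1 − 2^(−14/26) = 31% to 1 − 2^(−14/20) = 38%.

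**5. Size for chemotherapy, only if recording really stops.** A simulation used progression medians of 4 to 12 months, the Arm 2 scans (progression after week 52 taken as detected when it occurs) and a median delay of 2 to 6 months from detection to chemotherapy. If the hazard before detection is 10% to 25% of the later hazard, 35% to 91% of first-chemotherapy events within 104 weeks would be missed. If chemotherapy never precedes detection the share is 100%, but that follows by construction.

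**The case against.** The strongest reply is that this is loose wording and not a prescribed loss of data. Several parts of it stand.

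- A reader might infer that every man is removed at progression. The text gives the investigator a right, and its parenthesis mainly prevents removal for PSA alone. Removal is not automatic. The result would, however, depend on local practice across 4 to 5 centers.
- A reader might infer that chemotherapy, opioid use and skeletal events are all cut off just before they happen. Sections 5.5 and 6.7.1 expect the first two to be recorded later. Section 5.9.2.1 lists opioid use, fracture and cord compression as clinical progression in their own right, so they may come first. The documents give no ordering.
- A reader might put the share gone by weeks 26, 39 and 52 at 50–59%, 65–74% and 75–84%. Those are shares with underlying progression. Men would leave only when a scan detects it, and these draws fall at scan visits, so the preceding scan governs.
- A reader might infer that different scan weeks bias the arms against each other. With first sipuleucel-T at Arm 1 week 6, scans at weeks 16, 32, 45 and 58 fall 10, 26, 39 and 52 weeks after it, matching Arm 2. Arm 1 merely has about six more weeks at risk. Section 8.6.3 already plans interval-censored methods for the time-to-event secondary clinical endpoints.
- The chemotherapy, SRE and opioid endpoints are exploratory, and immune samples after progression would be confounded by later therapy.

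The synopsis ties the 3-monthly contacts to the last research visit without naming a week, which could include men who leave early. Section 3.0 and the schedule footnotes say week 58, so this does not settle the matter.

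**Conclusion.** The point holds as an unresolved conflict with two clear exposures. Sections 5.7.1 and 5.9 allow men to leave the study at radiographic progression without saying what continues, and do not fit with 3.0, 5.5 and 6.7.1. Skeletal events are the clearest gap: a fracture or cord compression after radiographic progression and after week 20, unrelated to treatment, has no dependable route into the data. The later immune samples are the second exposure, because nothing keeps progressed men in them and Section 8.6.3 states no missing-data approach.

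Under the stated assumptions, 23% to 29% of Arm 2 would be gone before week 26 and 50% to 59% before week 39. These figures are illustrative: the documents give no progression rate, and they assume that every progressor leaves. Censoring at progression would be informative, but the plan does not prescribe it; it gives no rule at all. The matter should be corrected, though it does not threaten the primary comparison.

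**What to change.** 1. Reconcile 5.7.1 and 5.9 with 3.0, 5.5 and 6.7.1 by using separate terms for coming off study treatment and coming off study. This concerns data collection only and changes no treatment rule.
2. State that consenting men with radiographic progression stay in the visits or 3-monthly contacts already scheduled, to the end of follow-up, for chemotherapy, opioid use, SRE and survival.
3. Add SRE to the follow-up list in Section 3.0 and to both schedules in 6.1, collected whatever its relation to treatment and beyond week 20.
4. State in 8.6.3 that these endpoints are not censored at radiographic progression, and give the censoring rule for each.
5. Make immune draws after progression optional, with subsequent therapy recorded. Report the late immune results with the number still contributing per arm at each visit, and state the missing-data approach.

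The cost is protocol wording and a few extra contacts for at most 34 men. Some will decline, particularly the 100 mL draws.
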